## GOALS

### 1.1. PRIMARY OBJECTIVE

To assess the safety of angioplasties performed in patients operated on at La Rochelle Hospital, these will be referred to as 12 monthsthen at 36 monthsafter the operation to find out if any major adverse cardiac events (MACE) have occurred since their operation. The MACE rate will thus be determined.

## RESEARCH DESIGN

This is non-interventional, cross-sectional, prospective, monocentric research.

## ELIGIBILITY CRITERIA

### 1.2. INCLUSION CRITERIA

- Patient treated for angioplasty,
- Person affiliated or beneficiary of a social security scheme,
- Informed about the study.

## **NON-INCLUSION CRITERIA**

- language barrier,
- Minor,
- Pregnant woman,
- Person under guardianship or curatorship,

- Persons deprived of liberty,
- Refusal to participate.

## FEASIBILITY AND MODALITIES OF RECRUITMENT

Participants will be selected from the Cardiology department of the Saint Louis Hospital of the La Rochelle-Ré-Aunis Hospital Group.

## **PROCEDURES STUDIED**

Patients referred for coronary angiography for revascularization are those diagnosed with acute coronary disease (Acute Coronary Syndrome with or without ST segment elevation) or chronic (silent myocardial ischemia, angina).

During coronary angiography, significant lesions are those for which the percentage of stenosis in relation to the reference diameter is  $\geq 50\text{-}70\%$ .

[figure not shown]
In case of angiographic doubt as to the significance of a lesion, an FFR (Fractional Flow Reserve) can be performed. A value less than or equal to 0.80 is thus in favor of a hemodynamically significant lesion.

Depending on the terrain, the number and the characteristics of the lesions, the patient is offered a strategy of surgical revascularization by bypass or interventional by angioplasty.

When the interventional strategy is chosen, the angioplasty of one or more lesions can be performed in one or more stages using stents (generally active) and/or active balloons.

The choice between stenting (active/naked) and active balloon is based on the following criteria:

- Active stenting:
  - hemodynamic instability, malignant ventricular hyperexcitability (VT, VF), plurivessel with altered LVEF,
  - extensive or sub-occlusive type C, D or E dissection or persistence of  $\geq 50\%$  stenosis after predilation.
- Active balloon: residual stenosis  $\leq 30\%$  and absence of extensive or sub-occlusive type C, D or E dissection after predilation(14), patient at risk of hemorrhage.
- Naked stenting: extensive or occlusive dissection after active balloon,

**Figure 1:** diagram of the strategy of revascularization by angioplasty.

\* In case of haemodynamic/rhythmic instability; FFR: Fractional Flow Reserve

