### **RESEARCH ASSUMPTIONS**

To assess the safety of angioplasties performed in patients operated on at La Rochelle Hospital, the rate of major adverse cardiac events (MACE) will be determined and analyzed in the light of data from the literature.

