### **EXPECTED BENEFITS**

The results of this study will make it possible to validate or not the algorithm of care applied to the hospital of La Rochelle.

The results will be communicated to the Coronary Atheroma and Interventional Cardiology Group (GACI).

[figure not shown]

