#### **1.3. STATISTICAL METHODS USED**

The parameters collected are presented in tables with descriptive statistics for the total population and for the sub-populations defined by the size of the vessels (small vessels / large vessels) or the procedure used (active stent[s] / stent [s] and balloon[s] active[s] / balloon[s] active[s]), according to the following modalities:

- For quantitative variables: the mean and the standard deviation or the median, the minimum and the maximum
- For qualitative variables: the number, percentages and 95% confidence interval, for each of the modalities of the variable (excluding missing data in the denominator).

The MACE rate will correspond to the ratio of the number of patients having had one or more MACE to the total number of patients for whom the follow-up was carried out at 12 months.then at 36 months.

To compare the sub-populations, the analyzes test the null hypothesis of equality of means for the quantitative variables and of homogeneity of the populations for the qualitative variables:

- For the quantitative variables, after checking the equality of the variances and the normal distribution of the values, the Student test is used. In case of inequality of variances or non-Gaussian distribution, a non-parametric Mann-Whitney/Wilcoxon test is used.
- For qualitative variables, a chi-square test is carried out or a Fisher test in the case of small numbers.

The study of risk factors for MACE is carried out by bivariate analysis. Odds ratios and 95% confidence intervals are calculated.

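### The MACE rate read against the literature is pooled over acute and chronic presentations, so part of any difference from a published series may reflect case mix

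*Combined protocol and SAP*

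**What the plan says.** Inclusion (section 1.2) asks only for "Patient treated for angioplasty", plus social security affiliation and information about the study. Procedures Studied describes the referred patients as "those diagnosed with acute coronary disease (Acute Coronary Syndrome with or without ST segment elevation) or chronic (silent myocardial ischemia, angina". ST-elevation ACS, non-ST-elevation ACS and chronic disease therefore all enter the cohort.

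For each of the two time points, 12 and 36 months, Statistical Methods Used (section 1.3) defines the MACE rate as "the ratio of the number of patients having had one or more MACE to the total number of patients for whom the follow-up was carried" (that is, completed). Descriptive tables are planned for the total population and "for the sub-populations defined by the size of the vessels (small vessels / large vessels) or the procedure used". Presentation is not among these sub-populations. On prognostic factors, the section says "The study of risk factors for MACE is carried out by bivariate analysis", with odds ratios and 95% confidence intervals. The factors are not listed, and no adjustment, weighting or standardisation is described.

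Research Assumptions, and the goals row of the summary, give the use of the result: "the rate of major adverse cardiac events (MACE) will be determined and analyzed in the light of data from the literature". Expected Benefits adds the consequence: "The results of this study will make it possible to validate or not the algorithm of care applied to the hospital of La Rochelle". No reference series, published rate, expected case mix or threshold is named for the comparison.

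**The concern.** The primary objective has no internal control, so the published rates are the only yardstick for the safety judgement. The composite endpoint includes death and myocardial infarction, whose risk may depend on how the patient presented as well as on the angioplasty. A crude rate is a weighted average of presentation-specific rates, with weights set by this centre's referral pattern. A published series has its own weights.

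If the acute share differs, the two crude rates can differ even when every presentation-specific rate is identical. The plan provides nothing that would separate that from a real difference in outcome.

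The planned device breakdown does not fill the gap. Procedures Studied lists haemodynamic instability and malignant ventricular arrhythmia among the criteria for one of the devices, so the device groups may themselves differ in acuity.

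**Working it through.** **Inputs from the documents.** Volume 1,252 patients in 2017 and planned size 1,000 (Study Size Calculation). Estimator: crude proportion among followed patients (section 1.3). The planned size reproduces as a recruitment count: 0.80 × 1,252 = 1,001.6, against 1,000 stated. It carries no precision target.

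**Inputs assumed.** The documents give no MACE rate by presentation, no acute share and no benchmark. I used acute/chronic MACE pairs from equal rates up to a threefold ratio, acute shares of 30%, 50% and 70%, and complete follow-up of 1,000 patients.

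**Formulas.** With acute share m, acute rate pA and chronic rate pC:

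- pooled rate = m × pA + (1 − m) × pC
- shift for a 20-point difference in m = 0.20 × (pA − pC)
- 95% half-width = 1.96 × √(p(1 − p)/1,000), taken at the 50% mix

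| Acute / chronic MACE | Pooled, 30% acute | Pooled, 50% acute | Pooled, 70% acute | Shift per 20 points of mix | 95% half-width |
|---|---|---|---|---|---|
| 8% / 8% | 8.0% | 8.0% | 8.0% | 0 | 1.7 |
| 8% / 6% | 6.6% | 7.0% | 7.4% | 0.4 | 1.6 |
| 10% / 5% | 6.5% | 7.5% | 8.5% | 1.0 | 1.6 |
| 12% / 5% | 7.1% | 8.5% | 9.9% | 1.4 | 1.7 |
| 15% / 6% | 8.7% | 10.5% | 12.3% | 1.8 | 1.9 |
| 15% / 5% | 8.0% | 10.0% | 12.0% | 2.0 | 1.9 |

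Example for 12%/5%: 0.5 × 12 + 0.5 × 5 = 8.5%; 0.7 × 12 + 0.3 × 5 = 9.9%; shift 1.4 points. Half-width 1.96 × √(0.085 × 0.915/1,000) = 1.7 points.

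**What such a shift could do to a comparison.** The plan specifies no test, so this is illustration only. Take a fixed benchmark with a 50% acute mix, a cohort at 30% or 70%, and a two-sided 5% one-sample test by normal approximation. With p0 and p1 the pooled rates in the benchmark and the cohort, the chance of a significant departure in the direction of the mix difference is Φ((|p1 − p0| − 1.96 × se0)/se1). It is 2.5% with no shift, about 7% to 8% at 8%/6%, 21% to 24% at 10%/5%, and 55% to 57% at 15%/5%.

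**Precision of the alternatives.**

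- Three equal strata of about 333 at 10%: 1.96 × √(0.10 × 0.90/333) = ±3.2 points.
- Standardised rate, with 300 acute at 12% and 700 chronic at 5% weighted to a 50/50 mix: 1.96 × √(0.25 × 0.12 × 0.88/300 + 0.25 × 0.05 × 0.95/700) = ±2.0 points. The crude rate in the same cohort (7.1%) has ±1.6 points.

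**The case against.** A reader might infer that case mix alone could make the centre look safe or unsafe. The documents do not support that. No benchmark, margin or test is specified, the formal primary objective (section 1.1) stops at determining the MACE rate, and no rule classifies the centre. What remains is the stated intention to read the rate against the literature and to draw a conclusion on the algorithm.

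A reader might also infer that the case-mix effect exceeds sampling error, because moving from 30% to 70% acute changes the pooled rate by 2.8 points at 12%/5% and 3.6 points at 15%/6%. Those figures need this centre and the literature to sit at opposite ends of an assumed 40-point gap, and they set a full range against a half-width. With a 20-point gap the shifts are 1.4 and 1.8 points, against half-widths of 1.7 and 1.9. At 8%/6%, even the full 40-point span gives only 0.8 points.

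Part of the gap may be filled in practice. If presentation is among the collected parameters, its distribution would be tabulated. If it is tested as a risk factor, the two-by-two table contains the presentation-specific rates. The factors are unlisted, so this is possible but not assured, and an odds ratio does not make the headline rate comparable with a published one.

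All-comer enrolment is legitimate for a descriptive cohort, and Procedures Studied is not at fault. Presentation is one of several possible case-mix differences, and the unnamed comparator is the more basic omission. Both remarks stand. Neither removes the point.

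**Conclusion.** The point holds in a limited form. Section 1.3 produces one crude rate over three presentations, Research Assumptions has that rate read against unspecified literature, and nothing in the plan stratifies or standardises by presentation. Part of any difference from a published series could therefore be case mix, and the analysis as planned could not show how much.

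The size cannot be derived from the documents. Under the assumptions above, a 20-point difference in acute share has an effect between zero and about the 95% half-width. It exceeds the half-width only with larger differences in mix or in rates, as at 15%/5%, where the shift is 2.0 points against 1.9. The crude rate remains a valid description of this cohort. The weak step is the inference drawn from comparing it with other cohorts. The same reasoning applies at 36 months, for which I have assumed no rates.

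**What to change.** In Statistical Methods Used (section 1.3), and in the matching row of the summary, add presentation as a sub-population: ST-elevation ACS, non-ST-elevation ACS and chronic. Report 12- and 36-month MACE with 95% confidence intervals for each, beside the overall rate.

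In Research Assumptions and the goals row of the summary, state that literature comparisons will be made within presentation, or after weighting this cohort's presentation-specific rates to the published series' mix, where that series reports what is needed. State that otherwise the pooled comparison is descriptive only.

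Sample size, eligibility and follow-up do not change. The cost is precision: about ±3.2 points per stratum at 10% with 333 patients, and a smaller loss if standardised rates are used. Two conditions apply. Presentation must be available from the inclusion record, which is assumed because Data Management names the entry software but lists no variables. The reference series must also be named, so that their mix can be checked.

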## EVALUATION CRITERIA

The primary endpoint is a composite endpoint of major adverse cardiac events defined as death, nonfatal myocardial infarction (MI), nonfatal stroke (stroke), and target lesion revascularization (TLR) within 12 months then 36 months following the intervention.

## **PROCEDURE OF THE RESEARCH**

### **RESEARCH TIMELINE**

- Duration of the inclusion period: 12 months
- Duration of follow-up per participant: 36 months (telephone contact at 12 monthsthen at 36 monthsfor MACE collection)
- Total search time: 48 month

### **SUMMARY TABLE OF PARTICIPANT MONITORING**

	Screening D-28 to D-1	Inclusion D0	Phone contact M12 +/- 30 days	Phone contact M36 +/- 30 days
Verification of eligibility criteria	X	X		
Presentation of the study	X	X		
Compendium of non-opposition		X		
MACE collection			X	X

### **INFORMATION OF DATA SUBJECTS**

The doctor offers the patient to participate in this research and informs him:

- of the objective,
- of the computerized processing of the data concerning him which will be collected during this research and also specifies his rights of access, opposition and rectification to this data.

The doctor also checks the eligibility criteria. If the person agrees to participate, they give their consent orally and their non-objection is documented in their medical file. The participant may, at any time, oppose the use of his data, within the framework of the research.

The non-objection is collected before the patient leaves hospital.

### **FOLLOW-UP VISITS**

Patients who have agreed to participate will be contacted one yearthen three yearsafter their intervention by telephone.

In case of MACE, the patient's cardiologist will be contacted for the detailed record of the event.

## **STATISTICAL ASPECTS**

### **STUDY SIZE CALCULATION**

In 2017, the La Rochelle cardiology department treated 1,252 patients for coronary pathologies. The objective is to include more than 80% of patients over a period of 12 months, ie 1000 patients.

#### **1.3. STATISTICAL METHODS USED**

The parameters collected are presented in tables with descriptive statistics for the total population and for the sub-populations defined by the size of the vessels (small vessels / large vessels) or the procedure used (active stent[s] / stent [s] and balloon[s] active[s] / balloon[s] active[s]), according to the following modalities:

- For quantitative variables: the mean and the standard deviation or the median, the minimum and the maximum
- For qualitative variables: the number, percentages and 95% confidence interval, for each of the modalities of the variable (excluding missing data in the denominator).

The MACE rate will correspond to the ratio of the number of patients having had one or more MACE to the total number of patients for whom the follow-up was carried out at 12 months.then at 36 months.

To compare the sub-populations, the analyzes test the null hypothesis of equality of means for the quantitative variables and of homogeneity of the populations for the qualitative variables:

- For the quantitative variables, after checking the equality of the variances and the normal distribution of the values, the Student test is used. In case of inequality of variances or non-Gaussian distribution, a non-parametric Mann-Whitney/Wilcoxon test is used.
- For qualitative variables, a chi-square test is carried out or a Fisher test in the case of small numbers.

The study of risk factors for MACE is carried out by bivariate analysis. Odds ratios and 95% confidence intervals are calculated.

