STATISTICAL ANALYSIS OF DATA	The parameters collected are presented in tables containing descriptive and comparative statistics (total population; small vessel/large vessel subpopulations; stent[s]/stent[s] and active balloon[s]/active balloons subpopulations assets]). The MACE rate corresponds to the ratio of the number of patients who had one or more MACE to the total number of patients for whom the follow-up was carried out at 12 monthsthen to36month. The study of risk factors for MACE is carried out by bivariate analysis.
EXPECTED BENEFITS	The results of this study will make it possible to validate or not the algorithm of care applied to the hospital of La Rochelle. The results will be communicated to the Coronary Atheroma and Interventional Cardiology Group (GACI).

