## **SCIENTIFIC RATIONALE AND GENERAL DESCRIPTION**

### **CURRENT STATE OF KNOWLEDGE**

Ischemic heart disease, or coronary heart disease, covers a set of pathologies due to insufficient oxygen supply to the myocardium due to the development of atherosclerosis in one or more coronary artery(ies). The use of active stents for the treatment of coronary stenosis is currently the standard treatment in almost all types of coronary lesions. In the percutaneous transluminal treatment of coronary artery lesions, balloon angioplasty with conventional balloons and drug-free eluting stents have not shown satisfactory results.(1)(2). Although some studies have shown balloon angioplasty and bare stent placement to be equally effective against restenosis(1)(2), a meta-analysis of 11 trials finds a rate of 25.8% for balloon angioplasty and 34.2% for bare-metal stents(3).

Thrombosis and in-stent restenosis, despite a decreasing incidence since the advent of first and then second generation active stents, remain frequent complications of angioplasty at around 5 to 15% depending on the series. (4.5). Indeed, the implantation of stents in the arterial wall leads to an inflammatory reaction around the mesh as well as the persistence of fibrinous deposits at the origin of a neointimal proliferation that is more thrombogenic than the native endothelium. (6). To this is added a phenomenon of neoatherosclerosis which appears later than on bare stents, most often 3 years from the date of implantation. On the other hand, very late stent thromboses, defined by the Academic Research Consortium as occurring more than one year after stent implantation, in fact require prolonged observation in order to take them into account.

The drug-eluting balloon, also called active balloon, or DCB (Drug Coated Balloon), was initially developed for the treatment of in-stent restenosis (4), and is currently considered the standard treatment for this pathology instead of in-stent active stenting. Since then, the active balloon has gradually been studied for the treatment of de novo lesions (5), particularly those of small vessels. The multicenter randomized BASKET-SMALL study on small de novo lesions (less than or equal to 2.5 mm in diameter) showed the non-inferiority of drug-eluting balloons compared to the active stent with regard to MACE up to 12 months, with similar event rates for both treatment groups(7).

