Recently, pilot studies have demonstrated the feasibility of using drug-eluting balloons for the treatment of bifurcations(8), chronic occlusions(9), as well as calcified lesions after Rotablator(10). These studies have thus shown very promising and consistent results when the active balloon was used as an alternative therapy. The German consensus group has therefore recently developed recommendations for the treatment of small vessel disease using the drug-eluting balloon(11).The BASKET SMALL 2 study is the first study to have compared the effectiveness of the active balloon versus an active stent in the treatment of de novo lesions of small vessels, with a fairly long follow-up period of 3 years and in a sufficiently large workforce. (12).Other studies have been able to demonstrate good results at 6 months in terms of efficacy and safety of the active balloon on the treatment of de novo lesions, regardless of the caliber of the vessel treated. (13). However, data are lacking in the literature concerning the treatment

of de novo lesions by active balloon, with a sufficiently long follow-up period to take into account neo-atheromatosis and very late stent thrombosis, in a large sample.

The use of drug-eluting balloons in La Rochelle has gradually evolved from the in-stent indication, to de novo lesions of small vessels ( $\leq 2.5$  mm), then to de novo lesions of large vessels. In addition to the treatment of long lesions on small caliber vessels, good immediate angiographic results are also obtained for the treatment of bifurcations (all types of Medina), for calcified lesions pretreated with Rotablator, as well as certain chronic occlusions.

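### Vessel size and procedure are analysed only as separate one-way splits, so no planned output gives the MACE rate of active balloons in large vessels, and the device contrast may be diluted or confounded by vessel size

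*Combined protocol and SAP*

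**What the plan says.** Section 1.3 (Statistical methods used) describes the total population and "sub-populations defined by the size of the vessels (small vessels / large vessels) or the procedure used". Procedure has three classes: active stent, stent plus active balloon, and active balloon. The Summary of research lists the same two splits side by side: "small vessel/large vessel subpopulations; stent[s]/stent[s] and active balloon[s]/active balloons subpopulations assets".

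Comparisons between sub-populations are unadjusted. For categorical outcomes such as MACE: "For qualitative variables, a chi-square test is carried out or a Fisher test in the case of small numbers". On predictors: "The study of risk factors for MACE is carried out by bivariate analysis". The outcome is a patient-level proportion: "The MACE rate will correspond to the ratio of the number of patients having had one or more MACE to the total number of patients", the denominator being those followed up at each time point. Neither place plans a crossed table, a stratified analysis, an interaction or a multivariable model.

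The section on the current state of knowledge says that "the active balloon has gradually been studied for the treatment of de novo lesions (5), particularly those of small vessels". It describes the centre's own use as moving from in-stent lesions to small de novo lesions, "then to de novo lesions of large vessels". The Expected benefits section says the results will serve to validate, or not, the centre's care algorithm.

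**The concern.** The protocol chose vessel size and device as its two analysis axes, but it does not combine them at the point where practice has moved furthest. Two size-specific rates and three procedure-specific rates do not determine the six crossed cells. A reader of the planned tables could not find the MACE rate for balloons in large vessels.

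There are two consequences:

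- **Dilution.** The balloon rate averages small and large vessels. An excess confined to one size is shrunk in the device contrast even when both device groups have the same size mix.
- **Confounding.** If the size mix differs by device and vessel size affects MACE, the unadjusted device odds ratio carries part of the size effect.

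The care algorithm could then be called validated without any reported rate for its newest use.

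**Working it through.** **The plan's own figure.** The section on study size takes more than 80% of 1,252 patients: 0.80 × 1,252 = 1,001.6, given as 1000. This reproduces. It is a recruitment count; no sub-population is sized and no MACE rate is assumed.

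**Planned outputs against the missing ones.** Planned: 2 size rates + 3 procedure rates. Crossed cells: 2 × 3 = 6, none planned.

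**Inputs.** The documents give no cell sizes, size mixes or MACE rates. All inputs below are assumptions chosen to show a range. Crude rate for a device = (share small × rate small) + (share large × rate large). OR = [p1/(1−p1)] / [p2/(1−p2)].

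**1. Confounding with no true device effect** (same rate for both devices within each size)

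| MACE small / large | Small-vessel share, balloon / stent | Crude balloon vs stent | OR |
|---|---|---|---|
| 12% / 8% | 50% / 50% | 10.0% vs 10.0% | 1.00 |
| 12% / 8% | 70% / 20% | 10.8% vs 8.8% | 1.25 |
| 15% / 8% | 70% / 20% | 12.9% vs 9.4% | 1.43 |
| 15% / 8% | 80% / 20% | 13.6% vs 9.4% | 1.52 |
| 10% / 10% | 70% / 20% | 10.0% vs 10.0% | 1.00 |

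Example, row 2: 0.7 × 12 + 0.3 × 8 = 10.8; 0.2 × 12 + 0.8 × 8 = 8.8; OR = (0.108/0.892)/(0.088/0.912) = 1.25. The distortion vanishes if the mixes are equal or if vessel size is not prognostic.

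**2. Dilution of a true 6-point excess in large vessels** (balloon 14%, stent 8%), with equal device rates in small vessels

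- Equal mix, 70% small in both groups, small-vessel rate 10%: 0.7 × 10 + 0.3 × 14 = 11.2%; 0.7 × 10 + 0.3 × 8 = 9.4%. Difference 1.8 points.
- Mix 70% / 20% small, small-vessel rate 10%: 11.2% vs 0.2 × 10 + 0.8 × 8 = 8.4%. Difference 2.8 points.
- Mix 70% / 20% small, small-vessel rate 7%: 0.7 × 7 + 0.3 × 14 = 9.1% vs 0.2 × 7 + 0.8 × 8 = 7.8%. Difference 1.3 points.

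Near-complete cancellation needs balloons to do better than stents in small vessels. With 7% vs 10% there: 9.1% vs 0.2 × 10 + 0.8 × 8 = 8.4%, a difference of 0.7 points and OR 1.09, against OR 1.87 in large vessels.

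**3. Precision of the missing cell** (Wilson 95% CI, assumed 10% MACE)

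| n in cell | 95% CI |
|---|---|
| 50 | 4.3-21.4% |
| 100 | 5.5-17.4% |
| 150 | 6.2-15.8% |
| 300 | 7.1-13.9% |

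**4. Power within large vessels** (two-sided 5%, 14% vs 8%, 400 stent patients assumed). Normal approximation with unpooled variance: power = Φ(0.06/SE − 1.96), SE² = 0.14 × 0.86/n + 0.08 × 0.92/400. This gives about 34% at n = 90 and 48% at n = 150.

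**The case against.** The strongest case against has four parts.

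1. The only stated objective is the overall MACE rate; the sub-populations are table breakdowns. This stands, and it limits the point to the secondary comparisons and to the care-algorithm aim.

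2. A reader might infer that the study is unable to give the rate for balloons in large vessels. The documents do not support that. Both factors define planned sub-populations, so both have to be recorded, and the crossed rate can be computed from the same database. What is missing is its pre-specification.

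3. A reader might also infer that the balloon group is mostly small-vessel, or that the device contrast is known to be confounded by size. No figure in the documents says so, and the Procedures studied section does not list vessel size among the criteria for choosing a device. The history of balloon use makes a difference in mix plausible, no more. Nor do the documents suggest that opposite device effects cancel: the rationale reports similar event rates for balloon and stent in small vessels.

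4. The rationale's evidence gap ("However, data are lacking in the literature concerning the treatment") concerns de novo lesions treated by balloon with long follow-up in a large sample, not large vessels alone, and it cites good 6-month results whatever the vessel calibre. So it goes too far to call this cell the least-established one. The newest step is also specifically de novo; a plain procedure-by-size cell would mix in balloons used for in-stent restenosis. Finally, crossing by size leaves the selection that the protocol does describe: instability, dissection, residual stenosis and bleeding risk. These objections stand and shape the fix.

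**Conclusion.** The point holds as a gap in the planned outputs. No planned table gives MACE for active balloons in large vessels. The unadjusted device contrast is averaged over vessel size and may be confounded by it if the mix differs by device. The primary estimate is not touched.

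Size, under assumed inputs only: a spurious device odds ratio between 1.00 and 1.52 where there is no true effect, and a 6-point large-vessel excess shrunk to between 1.3 and 2.8 points where small-vessel rates are equal. The missing cell does not depend on those assumptions; the direction and amount of any distortion do.

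The crossed analysis would be imprecise and, at the assumed cell sizes of 90 to 150, more likely than not to miss a 6-point difference. It should therefore be read as description. The change is worth making because it is cheap and because the results are meant to judge the care algorithm.

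**What to change.** In the Summary of research and in section 1.3:

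- Add a procedure-by-vessel-size table with number, percentage and 95% CI of MACE at 12 and at 36 months. Restrict it to de novo lesions, or show these separately, where lesion type is recorded.
- Report the balloon-only versus stent-only odds ratio stratified by vessel size (Mantel-Haenszel) with a test of homogeneity. Show the mixed-procedure class descriptively.
- Label this analysis exploratory, because selection by the criteria in the Procedures studied section remains. State that a non-significant result is not evidence of equal safety.
- State one vessel-size cut-off for analysis (2.5 mm appears only in the background) and one rule for patients treated in both vessel sizes. The existing size split already needs both.
- Base any conclusion on balloons in large vessels on that cell and its interval, not on the overall balloon rate.

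Cost: one table, one stratified analysis and two definitions, on factors the plan already uses. The price is wide cell intervals and low power within strata.

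### Device groups are formed by procedure used, so the balloon-only MACE rate is conditioned on no bail-out stent being needed, and bail-outs are pooled with planned combined treatment

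*Combined protocol and SAP*

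**What the plan says.** Section 1.3 (Statistical Methods Used) sets the device sub-populations by "the procedure used (active stent[s] / stent [s] and balloon[s] active[s] / balloon[s] active[s"). The Summary of Research gives the same three-way split: "stent[s]/stent[s] and active balloon[s]/active balloons subpopulations". In section 1.3 the first group is labelled as active stents, while the stent in the mixed group carries no such qualifier, so a bare stent fits there.

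The Procedures Studied section describes two routes into the mixed group:

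- Planned or staged combined treatment: angioplasty "can be performed in one or more stages using stents (generally active) and/or active balloons".
- Bail-out: "Naked stenting: extensive or occlusive dissection after active balloon".

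The same section makes the balloon conditional on a satisfactory predilation result, including "absence of extensive or sub-occlusive type C, D or E dissection after predilation".

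The MACE rate, computed at each of the two telephone contacts (one year and three years), is defined as "the ratio of the number of patients having had one or more MACE to the total number of patients for whom the follow-up was carried". Between sub-populations, "For qualitative variables, a chi-square test is carried out or a Fisher test in the case of small numbers". No adjustment is described: "The study of risk factors for MACE is carried out by bivariate analysis".

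No section states how a bail-out patient is classified, separates bail-out from planned combination, or groups patients by the strategy first started.

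**The concern.** Membership of the balloon-only group depends on something that happens after the balloon has been used. A patient whose only stent is a bail-out leaves that group because of an early result of the treatment. This is a different problem from baseline confounding: adjusting for baseline characteristics would not return those patients to the group, and the plan describes no adjustment in any case.

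Two rates become hard to interpret. The balloon-only rate describes patients in whom no bail-out was needed, not patients in whom a balloon was started. The mixed rate blends bail-outs with patients given a stent on one lesion and a balloon on another by design.

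This matters because the Expected Benefits section says the study will show whether the hospital's care algorithm is validated. That algorithm, as set out under Procedures Studied, includes the bail-out step. A rate that leaves bail-outs out does not describe the balloon branch of the algorithm.

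**Working it through.** **The plan's own figure.** The only related number is the sample size: 0.80 × 1,252 = 1,001.6, against 1,000 stated (1,000 / 1,252 = 79.9%). It reproduces, but it is a share of caseload. The documents give no device-group sizes, bail-out rate or expected MACE rate, so everything below except the classification rests on assumed inputs.

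**Classification, from the text alone.** Take a patient with one lesion, treated with an active balloon, then given a bare stent for dissection. Both devices were used. Of the three categories, only stent-and-balloon fits. A patient with a planned stent on another lesion is in that group already and does not move.

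**Balloon-only rate.** Let b be the bail-out share among balloon-started patients, p0 the MACE risk without bail-out and p1 the risk after bail-out.

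- Rate reported under the plan's grouping: p0
- Rate for the balloon-first strategy: (1 − b)·p0 + b·p1
- Understatement: b·(p1 − p0), which is zero when p1 = p0

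Assumed: 400 balloon-started patients with no planned stent, p0 = 8%, p1 = 16% or 24%.

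| b | Strategy rate, p1 = 16% | Strategy rate, p1 = 24% | Understatement (points) |
|---|---|---|---|
| 2% | 7.84 + 0.32 = 8.2% | 7.84 + 0.48 = 8.3% | 0.2 to 0.3 |
| 5% | 7.60 + 0.80 = 8.4% | 7.60 + 1.20 = 8.8% | 0.4 to 0.8 |
| 10% | 7.20 + 1.60 = 8.8% | 7.20 + 2.40 = 9.6% | 0.8 to 1.6 |
| 15% | 6.80 + 2.40 = 9.2% | 6.80 + 3.60 = 10.4% | 1.2 to 2.4 |

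The plan's grouping reports 8.0% in every row, a relative understatement of 2% (8.0 / 8.16) to 23% (8.0 / 10.4).

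**Against sampling error.** The 95% half-width is 1.96 × √(0.08 × 0.92 / n). It is 2.7 points at n = 392 (b = 2%) and 2.9 points at n = 340 (b = 15%).

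**Effect on an unadjusted test.** Suppose 400 stent patients have exactly the balloon-first strategy rate. The chance of a significant result favouring balloon-only is Φ((d − 1.96·SE0) / SE1), where d is the understatement, SE0 the pooled and SE1 the unpooled standard error. For b = 15%, p1 = 24%: (0.024 − 1.96 × 0.02142) / 0.02120 = −0.848, giving 20%. The other cases give 4% (b = 5%, p1 = 16%), 6% (10%, 16%) and 12% (10%, 24%). The nominal value in that direction is 2.5%.

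**Mixed group.** Assume 100 planned-combination patients at 10% MACE.

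- Adding 20 bail-outs at 16%: (10 + 3.2) / 120 = 11.0%.
- Adding 40 bail-outs at 24%: (10 + 9.6) / 140 = 14.0%.
- Adding 20 bail-outs at 8%: (10 + 1.6) / 120 = 9.7%.

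The mixed rate can therefore move either way, depending on the risk after bail-out.

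**The case against.** The strongest reply is that the only stated objective is the MACE rate for all angioplasties at the hospital. The device groups are sub-population tables with no hypothesis, power or decision rule attached, and grouping by devices used is a legitimate description in a non-interventional cohort. The first part stands: the primary rate is untouched. The second stands for a descriptive table, but section 1.3 also tests differences between these groups, and there the grouping rule matters.

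Several stronger readings are tempting, and the documents do not support them:

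- **That the grouping necessarily flatters the balloon.** The direction depends on a higher MACE risk after bail-out, and no document gives one.
- **That the balloon-only group contains only successes.** It is conditioned only on no stent being needed. Later death, infarction, stroke and target lesion revascularization in these patients still count.
- **That every bail-out changes group.** Patients with a planned stent elsewhere were already in the mixed group.
- **That the study exists to evaluate balloon-only treatment.** The rationale centres on the balloon, but the objective covers all angioplasties.

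It is also fair to say that the plan does not state in so many words that groups follow the devices finally used. That is the natural reading of its wording, and nothing in the text points the other way.

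**Conclusion.** The point holds as a defect in the device sub-population comparison. The classification follows directly from section 1.3 and Procedures Studied: a bail-out patient with no other stent leaves the balloon-only group and is pooled with planned combinations. That the balloon-only rate is conditioned on a post-treatment event needs no numerical assumption.

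The size and direction do. The understatement of about 0.2 to 2.4 points requires the assumed bail-out shares and the assumed two- to threefold MACE risk after bail-out. It falls to zero at equal risk, and across the range shown it is smaller than the confidence half-width of a group of this size. It is worth correcting because correction is cheap and the result bears on the care algorithm. A reader might infer that the study's main result is biased; it is not.

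**What to change.** In section 1.3 and in the statistical part of the Summary of Research, define mutually exclusive patient-level groups by the strategy started after predilation, across all index lesions and including staged procedures:

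- (a) active stent started on all treated lesions;
- (b) active balloon started on all treated lesions, including patients who then received a bail-out stent on a balloon-treated lesion;
- (c) stent started on at least one lesion and balloon on at least one other, whether or not a bail-out followed.

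Because the plan calls stents only generally active, list separately any patient who fits none of these, such as one started on a bare stent alone. Use these groups for the MACE comparison. Report the number and MACE rate of bail-out patients within (b) and (c), and keep the devices-used grouping as a secondary descriptive table.

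State alongside the results that (a) against (b) remains subject to selection at predilation and by clinical indication, and is not a causal device effect.

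The cost is a change of wording and a derived grouping variable, with no new patients or visits and no change to how devices are chosen. Device order per lesion must come from the index procedure record. The documents do not list the procedure variables, so availability has to be checked. The balloon result may look slightly less favourable.
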